9.4.2 TEAEs by Visit

TEAEs by CTCAE grade, treatment-emergent SAEs by CTCAE grade, and TEAEs leading to study withdrawal will be categorized by their start date. The two time categories will be (1) after Visit 1 and prior to the Visit 2 date and (2) after the Visit 2 date.

Page 23 of 38

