4.1.3 Administration Period

Administration of ¹²⁴I-AT-01 and the associated study procedures occur at the Day 1 and Week 6 (+ 2 week) visits. Administration of ¹²⁴I-AT-01 and the associated study procedures are described in Section 4.1.3.1.

4.1.3.1 Administration of Study Intervention(s) and Associated Procedures Day 1 and Week 6 (+ 2 week) Visits

The schedule for administration of ¹²⁴I-AT-01 is provided in the SoA (Section 1.3). Administration of ¹²⁴I-AT-01 occurs at the Day 1 and Week 6 to Week 8 visits, as follows:

Prior to Administration of ¹²⁴I-AT-01

- 1) Clinical laboratory tests and biomarker analysis (including serum pregnancy test in WOCBP) will be obtained within 7 days prior to the second administration of ¹²⁴I-AT-01, as described in the SoA (Section 1.3). The results of the pregnancy test must be available and be negative prior to ¹²⁴I-AT-01 administration in all WOCBP.
- 2) Instruct subject to take oral KI daily for 3 days, as described in Section 4.1.2.
- 3) Record concomitant medications and monitor and record AEs throughout the study visit.

Administration of ¹²⁴I-AT-01

4) Subjects enrolled under protocol Version 2.0 will receive a single dose of 1 mCi (± 10%) 124I-AT-01 by slow IV bolus at a rate of 1 mL/ 5 seconds. During 124I-AT-01 administration, monitor subjects for infusion-related reactions (IRRs), as described in Section 7.1.1. For all subjects, 124I-AT-01 will be administered by the same route (IV infusion over 2-5 minutes or slow IV bolus at 1 mL/5 seconds) at the Week 6 visit as on the Day 1 visit.

After Completion of Administration of ¹²⁴I-AT-01

- 5) Blood pressure and heart rate will be measured 5-10 minutes after administration of ¹²⁴I-AT-01.
- 6) Subjects will undergo a PET/CT scan 5 hours (± 30 minutes) after the start of administration of ¹²⁴I-AT-01 to quantify ¹²⁴I-AT-01 uptake in organs. ¹²⁴I-AT-01 whole-body scans will be acquired by study-designated PET/CT scanners, as described in Section 8.1.4.
 - Subjects will be discontinued if amyloid deposits are not identified in the Day 1 PET/CT scan in at least one of the following organs: heart, liver, spleen or kidney (i.e., they will not receive a second administration of ¹²⁴I-AT-01 or undergo a second scan) and will undergo early termination (ET) activities, as provided in the SoA (Section 1.3) and as described in Section 4.1.5.
- 7) Any adverse events will be recorded; patient can be discharged after completing the scan and deemed stable by study staff.

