6.6 Access to Study Intervention After End of Study

Administration of ¹²⁴I-AT-01 under this protocol will be completed at Visit 2 (Week 6 to Week 8). No further treatment with ¹²⁴I-AT-01 will occur under this protocol, and ¹²⁴I-AT-01 will not be made available to subjects by the Sponsor after completion of the study.

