3.2 Study Objectives

The primary study objective is to evaluate the repeatability of organ-specific quantitation of radiotracer uptake following PET/CT imaging of ¹²⁴I-AT-01 in subjects with AL or ATTR systemic amyloidosis.

The secondary study objective is to characterize the safety and tolerability of repeat doses of ¹²⁴I-AT-01 administered by intravenous (IV) infusion or slow IV bolus.

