8.1.2 Assessment Time Windows

The following study visits are scheduled:

Table 8-1: Assessment Time Windows

Visit	Analysis Visit Number	Window	Target Day
Screening	0	Day -30 to Day 1	N/A
Visit 1/Day 1	1	Day 1	1
Visit 2 /Week 6	2	After Day 1 to Week 8	43
Safety Follow-up 1	3	1-3 days after second infusion	1 day after second infusion date
Safety Follow-up 2/EOS/ET	4	28 (25-31) days after second infusion	28 days after second infusion date

All scheduled visits including assessments performed outside the target window, will be included in summary tables, figures, and listings. Scheduled visit data will be presented according to the nominal CRF recorded visit. Early termination visit and unscheduled visit data will be mapped to scheduled visits using the windows in Table 8-1. Early termination visit and unscheduled visit data will be included in tables and figures if no scheduled visit data is available for the nominal CRF recorded visit. If more than one unscheduled assessment (early termination or unscheduled) is performed within an analysis window for a visit without a nominal CRF record, the assessment performed closest to the target day will be used, if there is a tie, the earlier assessment will be used.

For clinical laboratory evaluation tables, early termination visits and unscheduled safety data will be mapped to scheduled visits using analysis windows. For all other safety tables and figures, early termination visits and unscheduled safety data will not be mapped to scheduled visits using analysis windows. All data, scheduled and unscheduled, will be included in listings.

Page 16 of 38

Version Date: 2022-12-16 Version: 2.0

Document Control No.: TMP-SA-008-01 Template Effective Date: 23 Mar 2021

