9.3 Adverse Events

Adverse events will be coded using the Medical Dictionary for Regulatory Activities (MedDRA) Version 24.1 to identify the system organ class and preferred term. All AEs and SAEs will be recorded from the time of informed consent until the final EOS telephone follow-up (~Week 10).

Treatment-emergent AEs are defined as events that are newly reported or reported to worsen in severity after the start of treatment. Adverse events that occur after the treatment start date, occur on the treatment start date with a time that is equal to or after treatment start time, or that have a missing AE start date will be categorized as treatment-emergent. Treatment-emergent AEs will be summarized for the Safety Set.

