9.4 Deaths, Serious Adverse Events, and Other Significant Adverse Events

Treatment-emergent SAEs, TEAEs leading to study withdrawal, and TEAEs resulting in death will be summarized separately for all subjects in the Safety Set. All percentages will use the number of subjects in the Safety Set as the denominator. Summary tables will reflect a count and percentage of subjects experiencing at least 1 TEAE in each system organ class and preferred term within each AE subset (serious, leading to study withdrawal, leading to death). The tabular summary will be sorted by descending frequency of system organ class and preferred term based on the overall incidence.

Records with missing SAE flags will be counted as SAEs.

Separate listing for SAEs, AEs leading to premature withdrawal from the study, and all deaths will be generated.

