14.3.1.5	Treatment-Emergent Serious Adverse Events by System Organ Class and Preferred Term	Safety
14.3.1.6	Treatment-Emergent Adverse Events Resulting in Study Withdrawal by System Organ Class and Preferred Term	Safety
14.3.1.7	Treatment-Emergent Adverse Events Resulting in Death by System Organ Class and Preferred Term	Safety
14.3.2.1	Summary of Treatment-Emergent Adverse Events on Day of Dosing by Visit	Safety
14.3.2.2	Treatment-Emergent Adverse Events on Day of Dosing by System Organ Class, Preferred Term, and CTCAE Grade by Visit	Safety
14.3.2.3	Summary of TEAEs by Visit	Safety
14.3.2.4	Summary of Hypersensitivity SMQ TEAEs by System Organ Class and Preferred Term by Visit	Safety
14.3.3.1	Laboratory Results: Chemistry	Safety
14.3.3.2	Laboratory Results: Hematology	Safety
14.3.3.3.1	Laboratory Results: Urine and Biomarker Results	Safety
14.3.3.3.2	Laboratory Results: Biomarker Result Categories	Image Evaluable Set
14.3.3.4	Clinically Significant Changes in Laboratory Values	Safety
14.3.4.1	Vital Sign Results	Safety
14.3.4.2	Clinically Significant Changes in Vital Signs	Safety

Page **35** of **38**

Version Date: 2022-12-16 Version: 2.0

Document Control No.: TMP-SA-008-01 Template Effective Date: 23 Mar 2021

Figures		
Number	Title	Population
14.2.1.1	Between Reader Bland Altman Plots of Difference in SUV metrics vs Average of SUV metrics by Visit and Organ	Image Evaluable
14.2.1.2	Between Reader Bland Altman Plots of Difference in SUV metrics vs Average of SUV metrics by Reader, Visit, and Organ and Amyloid Type	Image Evaluable
14.2.1.3	Between Visit Bland Altman Plots of Difference in SUV metrics vs Average of SUV metrics by Reader and Organ	Image Evaluable
14.2.1.4	Between Visit Bland Altman Plots of Difference in SUV metrics vs Average of SUV metrics by Reader and Organ and Amyloid Type	Image Evaluable
14.2.2	Signal to Noise Ratio vs SUV metrics by Reader, Visit, and Organ	Image Evaluable
14.2.3	Contrast to Noise Ratio vs SUV metrics by Reader, Visit, and Organ	Image Evaluable

Listings		
Number	Title	Population
16.2.1	Subject Disposition	All Subjects
16.2.2	Protocol Deviations	Safety
16.2.3.1	Inclusion/Exclusion Criteria Not Met	All Subjects
16.2.4.1	Demographics and Baseline Characteristics	Safety
16.2.4.2	Baseline Disease Characteristics	Safety
16.2.4.3.1	Medical History	Safety
16.2.4.3.2	Surgical or Procedural History	Safety
16.2.4.4	Prior and Concomitant Medications	Safety
16.2.4.5	Prior and Concomitant Medications - Amyloid	Safety

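### The by-visit adverse event tables compare unequal intervals after dose 1 and dose 2, probably over a common denominator, so their percentages are not comparable between doses and can mask a delayed re-exposure effect

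*SAP*

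**What the plan says.** SAP 3.2 states the aim: "The secondary study objective is to characterize the safety and tolerability of repeat doses". SAP 9.4.2 then sorts TEAEs by CTCAE grade, serious TEAEs by grade, and TEAEs leading to withdrawal according to when they began: "The two time categories will be (1) after Visit 1 and prior to the Visit 2 date and (2) after the Visit 2 date". The section gives no rule for interval length, person-time or denominator. The output is Table 14.3.2.3, "Summary of TEAEs by Visit", which SAP 15.1 assigns to the Safety population, as it does Tables 14.3.2.1, 14.3.2.2 and 14.3.2.4.

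The interval lengths come from elsewhere. Protocol 4.1.3.1 says that dosing "occurs at the Day 1 and Week 6 to Week 8 visits, as follows". SAP Table 8-1 places the final follow-up "28 (25-31) days after second infusion".

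On denominators, the parent section SAP 9.4 says: "All percentages will use the number of subjects in the Safety Set as the denominator". SAP 5 defines the Safety Set as everyone given any amount of tracer. Protocol 4.1.3.1 withholds dose 2 from subjects with no amyloid on the Day 1 scan, and Protocol 5.5 replaces subjects who do not receive dose 2. One-dose subjects are therefore expected by design.

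**The concern.** A reader who wants to know whether a second exposure is tolerated as well as the first will naturally set the two columns of Table 14.3.2.3 side by side. Events unrelated to dosing have longer to accrue after dose 1. If the Safety Set is the denominator, the dose 2 percentage is also diluted by people who were never exposed a second time.

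The stake is a delayed reaction on re-exposure. Protocol Table 1 lists immunogenicity as a risk, and SAP 9 places change in anti-drug antibodies outside its scope, so the by-visit hypersensitivity table (14.3.2.4) carries some weight. SAP 9.4.3 defines no time categories for that table, so its split is presumably the one in 9.4.2.

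**Working it through.** **Timeline check.** SAP 9.3 has adverse events recorded "until the final EOS telephone follow-up (~Week 10"). At target, 42 + 28 = 70 days = Week 10.0, which reproduces the plan's figure. The full windows give (42 + 25)/7 = 9.6 to (56 + 31)/7 = 12.4 weeks. With 30 days of screening, 100 days = 14.3 weeks, in line with the stated duration of about 14 weeks.

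**Interval lengths.** Category 1 is 42-56 days (41-55 if Day 1 is not counted). Category 2 is 25-31 days, target 28.
- Target: 42/28 = 1.50
- Smallest: 42/31 = 1.35
- Largest: 56/25 = 2.24

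**Effect on percentages.** The documents give no event rate, so the rates here are assumptions. Let b be the background risk of at least one TEAE per 28 days, constant over time. The chance of at least one event in t days is 1 - (1 - b)^(t/28).

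*No dose effect, everyone dosed twice, b = 20%, target windows:*
- Category 1: 1 - 0.8^1.5 = 28.4%
- Category 2: 1 - 0.8 = 20.0%
- Ratio 1.42, where the true ratio is 1.00

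For b from 10% to 60%, the ratio runs from 1.46 down to 1.25 at target windows. Over the extreme windows it spans 1.17 (42 against 31 days, b = 60%) to 2.12 (56 against 25 days, b = 10%).

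*Dose-related risk doubles.* Add a dose-related risk of 10% after dose 1 and 20% after dose 2. Assume onset after the dosing day but early enough to fall inside every window, with b = 20%.

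| Display | Dose 1 | Dose 2 |
|---|---|---|
| As planned (42 and 28 days) | 1 - 0.9 × 0.7155 = 35.6% | 1 - 0.8 × 0.8 = 36.0% |
| Equal 28-day windows | 1 - 0.9 × 0.8 = 28.0% | 36.0% |
| Equal 25-day windows (0.8^(25/28) = 0.8194) | 1 - 0.9 × 0.8194 = 26.3% | 1 - 0.8 × 0.8194 = 34.5% |

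The planned display shows almost no difference, although the dose-related risk has doubled.

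**Denominator.** Protocol 2.2.2 reports uptake in more than 90% of patients in the earlier study, so take 90% dosed twice as an illustration. If the Safety Set is the denominator, the 36.0% becomes 0.9 × 36.0% = 32.4%. If the other 10% leave 7 days after dose 1, category 1 becomes 0.9 × 35.6% + 0.1 × (1 - 0.9 × 0.8^0.25) = 33.5%. A doubling then appears as a slight decrease.

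**Purely acute events.** If all events occur in the first days after a dose, window length does not matter. Only the denominator does: a 20% risk at both doses shows as 20% against 0.9 × 20% = 18%.

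**Boundary.** Category 1 stops before the Visit 2 date and category 2 starts after it. An event on the Visit 2 date, including a reaction to dose 2 that day, meets neither condition. Whether post-dose events on Day 1 count as after Visit 1 is unclear. The doubling example avoids this problem by assuming onset after the dosing day.

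**The case against.** Several points on the other side stand.

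- **The table is not the endpoint.** The secondary endpoint is overall TEAE incidence from Day 1 to end of study, with laboratory values, vital signs and anti-drug antibodies. There is no hypothesis, and any p-values are descriptive. Neither document says the two intervals will be contrasted to judge which dose is safer.
- **Dosing-day events are covered.** SAP 9.4.1 summarises TEAEs starting on the day of dosing at each dosing visit, an equal one-day window per dose. Events on the Visit 2 date lost from Table 14.3.2.3 remain there. It does not capture later onset.
- **The denominator is inferred.** SAP 9.4.2 names none, the sentence in 9.4 sits with the tables on serious events, withdrawals and deaths, and table specifications are in separate documents. The Safety Set is the natural reading, not a stated rule. SAP 6.1 reports how many subjects received two doses, so a reader could rebuild that denominator, but not the windows.
- **Background may be low.** Protocol 10.3.1 excludes expected progression of the studied disease from the adverse event definition unless it is more severe than expected. Intercurrent illness remains, at an unknown rate.
- **Ascertainment runs the other way.** Protocol 4.1.4 schedules a call and a safety laboratory draw 1-3 days after dose 2, with no matching contact after dose 1. If only two thirds of category 1 events were captured, the event-count ratio at target would fall from 1.5 to 1.5 × 2/3 = 1.0. The real size is unknown, so it cannot be relied on as an offset.

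A reader might infer that dose 2 is bound to look safer, or that the repeat-dose safety objective is answered wrongly. The points above do not support either conclusion.

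**Conclusion.** The point holds as a defect of presentation, minor to moderate. The intervals differ by a factor of 1.5 at target (1.35-2.24), nothing in SAP 9.4.2 corrects for it, and the boundary wording drops Visit 2 date events from the table. By-visit percentages produced as written are not comparable between doses. They under-represent background events after dose 2 and can mask an increase on re-exposure that begins after the dosing day.

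The interval arithmetic is firm. The size of the distortion is not: it rests on assumed background and dose-related rates, an assumed share dosed twice, an inferred denominator, and equal capture of events in both intervals. Where events are mainly acute, little of the distortion remains beyond the denominator effect. Overall TEAE incidence is untouched.

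**What to change.** In SAP 9.4.2, and by reference for Table 14.3.2.4 under 9.4.3:

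1. Start each category at the start of that administration, so that dosing-day events after the start of dosing are counted under the dose that preceded them.
2. Use the same post-dose window for both doses, for example through 25 days, the shortest planned follow-up after dose 2.
3. Show dose 1 events that start after the window, and before dose 2, in a separate row.
4. In Tables 14.3.2.1 to 14.3.2.4, use the number of subjects who received the tracer at that visit as the denominator, and say so in the SAP.

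Subjects who leave soon after dose 1 will still have short follow-up in its window. A footnote giving the number followed through the window for each dose would make that visible.

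The cost is SAP wording, revised table shells and one extra row. No data collection or visit changes.

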9.4.3 Hypersensitivity AEs

Hypersensitivity TEAEs will also be summarized by SOC and preferred term. Hypersensitivity TEAEs are all the preferred terms in the Standardized MedDRA Queries (SMQs) of Hypersensitivity (narrow scope).

9.5 Clinical Laboratory Evaluation

Baseline for clinical chemistry parameters is defined as the most recent laboratory measurement obtained prior to the initiation of study drug. The post-baseline visits are Visit 2 / Week 6 and Safety Follow-up 1 (1-3 days after the second infusion).

Baseline and all post-baseline visit values and change from baseline to post-baseline in laboratory parameters for clinical labs will be summarized for the Safety Set using descriptive statistics, as described in Section 4. Unscheduled visits will be mapped to scheduled visits using analysis windows according to Section 8.1.2.

Biomarkers include NT-proBNP, brain natriuretic peptide (BNP), serum free light chains (only subjects with AL amyloidosis), UACR (only subjects with AL amyloidosis), FLC ratio (Kappa/Lambda) (only subjects with AL amyloidosis), and dFLC (only subjects with AL amyloidosis).

Serum chemistry, Hematology, and biomarker assays will also be presented in data listings for subjects in the Safety Set. The listing will include the reference range (if applicable), classification of high, low, critical, or exclusion, and an abnormal flag. Classification of laboratory values and reference ranges in the data listings will be based on the global laboratory reference ranges used across all sites.

Laboratory parameters with clinically significant changes will be summarized and listed as 'flagged' based on the Sponsor's internal guidelines based on Appendix 14.3.

Additional categorizations of biomarker results for the Image Evaluable Set will be produced including the number and percentage of subjects with:

- Screening and Visit 2 NT-proBNP < 650 ng/L
- Screening or Visit 2 NT-proBNP >= 650 ng/L
- Screening or Visit 2 NT-proBNP >= 650 ng/L and change in NT-proBNP of >= 30% and >= 300 ng/L from Screening to Visit 2
- Screening or Visit 2 NT-proBNP missing
- AL subjects with a normal FLC ratio at Screening and Visit 2

This summary will also include descriptive statistics for dFLC in AL subjects with an abnormal FLC ratio at Screening or Visit 2. NT-proBNP will be displayed in ng/L using the conversion: 1 ng/L = 8.457 pmol/L.Pregnancy test results will also be presented in a data listing for the Safety Set.

Page 24 of 38

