1.3 Schedule of Activities

| Visit | Screening | Vis Da | it 1/ y 1 | | it 2/ ek 6 | Safety Follow-up 1 ^j | Safety Follow-up 2 (EOS) ^j | Early Termination (ET) k,l |
|--|------------------------|---------------------------------|------------------------------------|---------------------------------|------------------------------------|------------------------------------|---|--------------------------------|
| Window | Day -30 to Day 1 | ± 0 | days | Week 6 t | o Week 8 | 1-3 Days After Visit 2 | 28 (± 3) Days After Visit 2 | <7 days from ET Decision |
| Timing of Activity(ies) | | Prior to ¹²⁴ I-AT-01 | ¹²⁴ I-AT-01 and Scan | Prior to ¹²⁴ I-AT-01 | ¹²⁴ I-AT-01 and Scan | | | |
| Assessment/Procedures | | | | | | | | |
| Informed Consent a | X | | | | | | | |
| Medical history and Demographics | X | | | | | | | |
| Inclusion and Exclusion criteria | X | | | | | | | |
| Concomitant Medications | X | X | X | X | X | X | X | X |
| Oral Potassium Iodide (KI) ^b | | X | | X | | | | |
| ¹²⁴ I-AT-01 Administration ^c | | | X | | X | | | |
| Biomarker and Safety Assessments | | | | | | | | |
| Vital Signs (HR and BP) d | | X | X | X | X | | | |
| Body Weight | | X | | X | | | | |
| Height | | X | | | | | | |
| Pregnancy Test (WOCBP) e,f | X | | | X | | | | |
| PET/CT Scan | | | X | | X | | | |
| Adverse events g | X | X | X | X | X | X | X | X |
| Laboratory h,i | X | | | X | | X | | |
| Biomarkers h,i | X | | | X | | | | |
| Urine UACR (AL subjects only) i | X | | | X | | | | |
| Serum ADA i | X | | | X | | | X | X |

Abbreviations: ADA = anti-drug antibodies; AL = amyloid light chain amyloidosis; BP = blood pressure; CBC = complete blood count; EOS = end of study; ET = early termination; HR = heart rate; NT-proBNP = N-terminal prohormone of brain natriuretic peptide; UACR = urine albumin-to-creatinine ratio; WOCBP = women of childbearing potential.

- a. Informed consent, as described in Section 10.1.3.
- b. KI is self-administered by the subject daily for 3 days, beginning >30 minutes and <24 hr prior to dosing, as described in Section 4.1.2.
- c. ¹²⁴I-AT-01 will be administered by IV infusion over 2-5 minutes (protocol Version 1.1) or slow IV bolus at 1 mL/5 seconds (protocol Version 2.0), as described in Section 4.1.3. For all subjects, ¹²⁴I-AT-01 will be administered by the same route (IV infusion over 2-5 minutes or slow IV bolus at 1 mL/5 seconds) at the Week 6 visit as on the Day 1 visit.

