- d. Subjects must remain semi-recumbent for at least 5 minutes prior to blood pressure measurements. Blood pressure and heart rate will be measured within an hour prior to dosing and 5-10 minutes after administration of ¹²⁴I-AT-01.
- e. Serum pregnancy test, as indicated in Section 10.2, will be obtained in all women of childbearing potential.
- f. Serum pregnancy and all other laboratory samples must be drawn within 7 days prior to administration of ¹²⁴I-AT-01 in all WOCBP. The results of the pregnancy test must be available and be negative prior to ¹²⁴I-AT-01 administration in all WOCBP.
- g. Adverse events will be monitored from Screening through the EOS Visit. For Safety Follow-up 1 and 2, adverse events and concomitant medications can be obtained by phone call.
- h. Clinical laboratory tests and biomarker analysis, as described in Section 10.2. Baseline sample will be collected within 30 days prior to the first administration of ¹²⁴I-AT-01; second sample within 7 days prior to the second administration of ¹²⁴I-AT-01; third sample at Safety Follow-up 1 after the second administration of ¹²⁴I-AT-01.
- i. Urine and blood may be collected locally by visiting nurse/phlebotomist. An additional serum ADA sample will be obtained at Screening for subjects who provided consent for the extra ADA sample.
- j. Safety follow-ups for concomitant medications and adverse events will be done via telephone call for all subjects. Both Safety Follow-up 1 and Safety Follow-up 2 activities will be conducted for subjects who discontinue for IRRs at either the first or second administration of ¹²⁴I-AT-01.
- k. Blood draw for ADA should be obtained if ET is ≥4 weeks after first administration of ¹²⁴I-AT-01.
- l. Early Termination activities do not apply to subjects discontinued for IRRs. Please follow Safety Follow-up 1 and Safety Follow-up 2 activities for subjects experiencing IRR with either the first or second administration of ¹²⁴I-AT-01.

- 15 -

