9 SAFETY EVALUATION

The secondary study objective is to characterize the safety and tolerability of repeat doses of ¹²⁴I-AT-01 administered by IV infusion or slow IV bolus. The key secondary endpoints are incidence of treatment-emergent AEs from Day 1 to EOS, change from baseline in clinical laboratory values at Visits 2 and Safety Follow-up 1 (1-3 days after the second infusion), change from baseline in vital signs, and change from baseline in anti-drug antibodies (ADA).

Change from baseline in ADA is outside the scope of this SAP.

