- f. Serum pregnancy and all other laboratory samples must be drawn within 7 days prior to administration of ¹²⁴I-AT-01 in all WOCBP. The results of the pregnancy test must be available and be negative prior to ¹²⁴I-AT-01 administration in all WOCBP.
- g. Adverse events will be monitored from Screening through the EOS Visit. For Safety Follow-up 1 and 2, adverse events and concomitant medications can be obtained by phone call.
- h. Clinical laboratory tests and biomarker analysis, as described in Section 10.2. Baseline sample will be collected within 30 days prior to the first administration of ¹²⁴I-AT-01; second sample within 7 days prior to the second administration of ¹²⁴I-AT-01; third sample at Safety Follow-up 1 after the second administration of ¹²⁴I-AT-01.
- Urine and blood may be collected locally by visiting nurse/phlebotomist. An additional serum ADA sample will be obtained at Screening for subjects who provided consent for the extra ADA sample.
- j. Safety follow-ups for concomitant medications and adverse events will be done via telephone call for all subjects. Both Safety Follow-up 1 and Safety Follow-up 2 activities will be conducted for subjects who discontinue for IRRs at either the first or second administration of ¹²⁴I-AT-01.
- k. Blood draw for ADA should be obtained if ET is ≥4 weeks after first administration of ¹²⁴I-AT-01.
- Early Termination activities do not apply to subjects discontinued for IRRs. Please follow Safety Follow-up 1 and Safety Follow-up 2 activities for subjects experiencing IRR with either the first or second administration of ¹²⁴I-AT-01.

Page 31 of 38

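### Safety Follow-up 1 laboratory results are labelled as second-dose data, yet the visit is also required after a first-dose infusion-reaction discontinuation; a change from the Visit 2 pre-dose sample would be a free addition.

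*SAP*

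**What the plan says.** The laboratory row of the Schedule of Activities (Protocol 1.3, repeated in SAP 14.2) has three marks: Screening, Visit 2 before dosing, and Safety Follow-up 1. Nothing is scheduled on Day 1, at Safety Follow-up 2 or at Early Termination. Footnote h sets the windows: "Baseline sample will be collected within 30 days prior to the first administration of ¹²⁴I-AT-01", then "second sample within 7 days prior to the second administration of ¹²⁴I-AT-01", then a third sample at Safety Follow-up 1.

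SAP 9 names as a secondary endpoint "change from baseline in clinical laboratory values at Visits 2 and Safety Follow-up 1 (1-3 days after the second infusion", and SAP 9.5 repeats the timing: "The post-baseline visits are Visit 2 / Week 6 and Safety Follow-up 1 (1-3 days after the second infusion". SAP Table 8-1 and Protocol 7.1.1.1 also place the visit relative to the second dose only.

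Footnote j of the same schedule says that the activities of both safety follow-ups "will be conducted for subjects who discontinue for IRRs at either the first or second administration". Footnote l and Protocol 4.1.4 and 4.1.5 agree.

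On assigning data to visits, SAP 8.1.2 says: "Scheduled visit data will be presented according to the nominal CRF recorded visit". For laboratory tables, unscheduled and early termination samples are mapped by the Table 8-1 windows, where the Visit 2 window opens straight after Day 1 and runs to Week 8. The laboratory summaries use the Safety Set, which takes in anyone given any amount of tracer (SAP 5).

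Baseline is the last value before the first dose (SAP 4 and 9.5; Protocol 9.5.4). Change from that value is the only laboratory change planned. SAP Appendix 14.3 lists the rises and falls that count as clinically significant but does not say from which value they are measured.

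**The concern.** Two things are at stake in the one sample that can show an acute laboratory effect.

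First, a subject stopped for an IRR at the first administration has no second administration, so the visit's stated timing cannot apply. The SAP still gives the sample nowhere to go except a column whose label is untrue for it. Such a subject is also selected for having reacted, so a result from that subject should not be read as a typical response to the second dose. The SAP does separate adverse events by dosing visit (9.4.1 and 9.4.2), but not laboratory data.

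Second, for subjects who do receive the second dose, the change at Safety Follow-up 1 covers the whole interval since before the first dose. It therefore combines any acute effect of the second dose with weeks of disease course and background treatment, although a sample taken shortly before that dose exists.

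**Working it through.** The documents state no figure for these intervals, so there is none to reproduce. The check is calendar arithmetic on their own windows, plus tracing one subject through the visit rules.

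**Inputs**
- Baseline sample: 0 to 30 days before dose 1 (footnote h). For women of childbearing potential, all laboratory samples fall within 7 days before dosing (footnote f; Protocol 4.1.1).
- Dose 2: Week 6 to Week 8. SAP Table 8-1 sets the Week 6 target at Day 43 = Day 1 + 42, so the range is 42 to 56 days after dose 1.
- Visit 2 sample: 0 to 7 days before dose 2 (footnote h).
- Safety Follow-up 1: 1 to 3 days after dose 2.

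**Step 1. Which scheduled samples closely follow a dose?** The Visit 2 sample falls 42 − 7 = 35 to 56 − 0 = 56 days after dose 1. Safety Follow-up 1 falls 1 to 3 days after dose 2. Only the latter is scheduled within days after a dose.

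**Step 2. A subject who discontinues for an IRR at dose 1**
- Footnotes j and l exempt the subject from the Early Termination activities and require Safety Follow-up 1, which includes the laboratory draw.
- The subject received tracer, so is in the Safety Set.
- If the site records the sample as Safety Follow-up 1, the nominal-visit rule keeps it there, under a second-infusion label.
- If the site records it as unscheduled or early termination, a sample drawn soon after Day 1 falls in the Visit 2 window. With no scheduled Visit 2 record to displace it, it is tabulated as Visit 2/Week 6.
- No route leads to a correct label.

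**Step 3. Size of the mislabelling.** One subject in a 20-subject column is 1/20 = 5%. The documents give no rate of first-dose IRR discontinuation.

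**Step 4. Distance to the reference value, for subjects who receive dose 2**
- Baseline to Safety Follow-up 1, minimum: 0 + 42 + 1 = 43 days.
- Maximum: 30 + 56 + 3 = 89 days (88 if Week 8 is read as Day 56).
- Maximum for women of childbearing potential: 7 + 56 + 3 = 66 days.
- Visit 2 sample to Safety Follow-up 1: 0 + 1 = 1 to 7 + 3 = 10 days.

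**Step 5. What the choice of reference can do to a flag.** Take invented haemoglobin values of 11.5 g/dL at Screening, 13.5 at Visit 2 and 10.6 at Safety Follow-up 1, and assume that 10.6 is below the lower limit of normal. From baseline the change is (10.6 − 11.5)/11.5 = −7.8%. From the Visit 2 sample it is (10.6 − 13.5)/13.5 = −21.5%. The Appendix 14.3 criterion (a fall above 20%, to below the lower limit) is met only with the second reference. This shows the mechanism and says nothing about frequency.

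**The case against.** The strongest reply concerns the comparator. The stated endpoint is change from baseline, baseline is defined as before study drug, and the SAP does exactly that. The study has no hypothesis, and its safety output is descriptive. Visit 2 and Safety Follow-up 1 values are both summarised, and with up to 20 subjects the change between them can be read from the listings. All of this stands. A reader might infer that the SAP analyses the endpoint wrongly; the documents do not support that. The added comparison is an improvement only.

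On the label, the reply is that it matters only if someone discontinues for an IRR at the first dose, and only through how the site records the sample. The first condition is right, and the number may be zero. It would be wrong to count every subject who reacts to the first dose, because one whose symptoms resolve promptly may continue (Protocol 7.1.1.1). The second condition does not rescue the plan, because each recording route ends in a wrong label. It is also fair that the problem starts in the protocol, which carries the same second-administration wording, so a change to the SAP alone would not resolve it.

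Three other readings go too far. Safety Follow-up 1 is not the only laboratory sample near a dose: the Visit 2 sample precedes dose 2 by at most 7 days, and unscheduled tests are allowed (Protocol 8.2.2). The 89 days is a maximum that applies neither to women of childbearing potential nor to first-dose discontinuations. Lastly, no gain in precision from the nearer reference can be stated, because the documents give no within-subject correlations. The haemoglobin values are contrived: a rise of 2.0 g/dL by Visit 2 and then a fall of 2.9 g/dL.

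**Conclusion.** The labelling point holds. The documents require Safety Follow-up 1 after a first-dose IRR discontinuation, define its timing only by the second dose, and give the resulting sample no correct analysis visit. Its size is about 5% of a 20-subject column for each such subject, for a number of subjects that is unknown and may be zero.

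The comparator point is an inexpensive improvement and not an error. The planned reference is 43 to 89 days old (at most 66 for women of childbearing potential), against 1 to 10 days for a sample already scheduled. These intervals assume that visits and samples fall within their windows, with Week 8 read as 56 days after dose 1. That Appendix 14.3 is measured from baseline is the natural reading under SAP 4, but the appendix does not say so.

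Both points concern descriptive safety tables for a secondary endpoint. The primary repeatability analysis is unaffected.

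**What to change.** 1. Reconcile Protocol 1.3 (footnotes j and l), 4.1.4, 4.1.5 and 7.1.1.1 with SAP 9, 9.5 and Table 8-1, so that the timing of Safety Follow-up 1 is defined for subjects who discontinue at the first administration. The documents give no such window, and choosing one is for the sponsor.
2. In SAP 8.1.2 and 9.5, and in Tables 14.3.3.1, 14.3.3.2 and 14.3.3.4, report these subjects' samples under a separate post-first-administration analysis visit, outside the second-dose column and outside Visit 2/Week 6. The visit can be derived from the recorded dosing dates (SAP 9.2), however the site labels the sample.
3. Keep change from baseline as the stated endpoint. In the same tables, add change from the Visit 2 pre-dose sample to Safety Follow-up 1, and apply the Appendix 14.3 change criteria to it as well.
4. State in Appendix 14.3 the reference value for each change criterion.

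The cost is a protocol clarification, SAP wording and a few table rows. No new sample is needed.
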